### **10.9 ADVERSE EVENTS MONITORING**

All events will be managed and reported in compliance with all applicable regulations and included in the final clinical study report.

## 11 STATISTICAL CONSIDERATIONS

### 11.1 DETERMINATION OF SAMPLE SIZE

The sample size calculations are based on the primary efficacy variable of sustained remission at Week 52 compared between the sarilumab and placebo groups. There are no prior controlled study data to establish the placebo remission rate in PMR. A 25% difference from placebo response rate is considered clinically relevant, and the initial sample size of 140 per group provides at least 90% power to detect such a difference regardless of the placebo response rate, using a two-sided  $\chi^2$  test at a significance level of 0.01. Data from the GIACTA trial in a related population with GCA suggest that such a treatment difference is achievable (22).

As a result of the inability to recruit due to the COVID19 pandemic, the power calculations have been revised for the decreased sample size from 140 per group to 59 per group, and the change in statistical significance level from 0.01 to 0.05.

Table 3 shows the power calculations for sample size of 118 based on a two-sided  $\chi^2$  test at a significance level of 0.05. The sample size of 59 per group provides at least 85% and 95% power to detect a 25% and 30% between group difference respectively, assuming placebo response rates between 5% to 15%.

### 11.2 DISPOSITION OF PATIENTS

Screened patients are defined as any patient who signed informed consent.

Randomized patients consist of all patients, with signed informed consent, with a treatment kit number allocated and recorded in the IRT database, regardless of whether the treatment kit was used or not. These patients form the randomized population.

Patients treated without being randomized will not be considered as randomized and will not be included in any efficacy population.

For any patient randomized more than once, only the data associated with the first randomization will be used in any analysis population. The safety experience associated with any later randomization will be assessed separately.

The safety experience of patients treated and not randomized will be reported separately, and these patients will not be in the safety population.

## **11.3 ANALYSIS POPULATIONS**

### **11.3.1 Efficacy populations**

#### ***11.3.1.1 Intent-to-treat /modified intent-to-treat population***

Intent-to-treat (ITT) population: all randomized population analyzed according to the treatment group allocated by randomization. All efficacy analyses will use this population.

#### **11.3.2 Safety population**

Safety population: all randomized patients who have received at least one dose or part of a dose of the study medication (IMP) analyzed according to the treatment they have actually received.

In addition:

- Non-randomized but treated patients will not be part of the safety population, but their safety data will be presented separately.
- Randomized patients for whom it is unclear whether they took the study medication will be included in the safety population as randomized.
- For patients receiving more than 1 study treatment during the trial, the treatment group allocation for as-treated analysis will be the treatment for which the patient received the majority of doses.

#### **11.3.3 Pharmacokinetic analysis population**

The PK population will consist of all patients in the safety population with at least one post-dose, non-missing serum sarilumab concentration.

The ADA population will consist of all patients in the safety population with at least one non-missing ADA result in the ADA assay following the first dose of the study medication.

## **11.4 STATISTICAL METHODS**

Analysis of the randomization double-blind phase is described below. The post-treatment follow-up phase will be presented separately without formal statistical testing, and details of the follow-up phase will be provided in the SAP.

### **11.4.1 Extent of study treatment exposure and compliance**

The extent of study treatment exposure and compliance will be assessed and summarized by actual treatment received within the safety population.

#### **11.4.1.1 Extent of investigational medicinal product exposure**

Duration of sarilumab exposure is defined as: last double-blind dose date – first double-blind dose date +14 days, regardless of unplanned intermittent discontinuations.

Duration of exposure to the double-blind IMP (sarilumab or matching placebo) will be summarized for each treatment group descriptively as a quantitative variable (N, Mean, standard deviation [SD], Median, Min, and Max).

In addition, the number and percentage of patients randomized and exposed to the double-blind IMP will be presented by specific time periods for each treatment group.

#### **11.4.1.2 Compliance**

Treatment compliance to the double-blind IMP (sarilumab or matching placebo) is defined as the actual amount of injections received compared to the scheduled amount of injections during the double-blind treatment period. It is calculated according to the following formula:

$100 \times \text{total number of injections administered} / [\text{nominal number of injections for the duration of double-blind exposure}]$ .

A given administration will be considered noncompliant if the patient did not take the planned dose of injection as required by the protocol. No imputation will be made for patients with missing or incomplete data.

Treatment compliance, above-planned and under-planned dosing percentages will be summarized descriptively (N, Mean, SD, Median, Min, and Max). The percentage of patients with compliance is <80% will be summarized. In addition, number and percentage of patients with at least 1 above-planned dosing administration will be given, as well as the number and percentage of patients with 0, (0, 20%), and >20% under-planned dosing administrations.

### **11.4.2 Analyses of efficacy endpoints**

#### **11.4.2.1 Analysis of primary efficacy endpoint(s)**

The primary endpoint (refer to [Section 9.1.1](#)) is the proportion of patients achieving sustained remission at Week 52 compared between sarilumab and placebo analyzed in the ITT population. The primary endpoint will be summarized as counts and proportions in each treatment group and analyzed by Fisher's exact test. Patients who do not achieve remission, receive rescue treatment with open label prednisone (or equivalent), withdraw from the study before Week 52, or having missing data that prevents assessment of the primary endpoint will be considered as non-responders. The significance level for all tests will be 0.05 (2-sided).

Sensitivity analyses will be performed based on a revised remission definition excluding acute phase reactants.

#### **11.4.2.2 Analyses of secondary efficacy endpoints**

Other binary endpoints (defined in [Section 9.2.1](#)) will be analyzed as described for the primary endpoint (see [Section 11.4.2.1](#)).

The cumulative prednisone (or equivalent) dose will be analyzed using a non-parametric Wilcoxon rank-sum test and the mean and median dose summarized.

Time events will be analyzed by Kaplan-Meier method. Treatment groups will be compared with the use of Cox proportional hazards models. Data censoring will be used for patients who withdraw from the study.

The GTI assessment (total score and domain-specific scores) will be analyzed as other secondary efficacy endpoint using the mixed model repeated measures (MMRM) approach. The model includes treatment, visit, treatment-by-visit interaction as fixed effects, and baseline score as a covariate, will be used to test the difference of the least-square means (LS means) between treatment groups. Descriptive statistics including number of subjects, mean, standard error and LS means will be provided. In addition, difference in LS means, the corresponding 95% CI and the p-value will be provided.

#### **11.4.2.3 Multiplicity considerations**

If the primary endpoint reaches statistical significance, then secondary endpoints will be tested in a fixed sequential order to maintain an overall type I error rate of 0.05. Details of the hierarchical testing approach will be specified in the statistical analysis plan.

#### **11.4.3 Analyses of safety data**

The summary of safety results will be presented by treatment group. Incidence rates and exposure adjusted event summaries will be provided for categorical safety summaries.

All safety analyses will be performed on the safety population using the following common rules:

- The baseline value is defined generally as the last available value before randomization.
- The observation period to be used for the safety population is the TEAE period. The TEAE period is defined as the time from first dose of randomized study treatment to the last dose date of IMP +60 days.
- For quantitative safety parameters based on central laboratory/reading measurements, descriptive statistics will be used to summarize results and change from baseline values by visit and treatment group.
- The analysis of the safety variables will be essentially descriptive and no hypothesis testing is planned.

The following definitions will be applied to laboratory parameters, vital signs and ECG.

- The potentially clinically significant abnormality (PCSA) values are defined as abnormal values considered medically important by the Sponsor according to predefined criteria/thresholds based on literature review and defined by the Sponsor for clinical laboratory tests, vital signs, and ECG.
- PCSA criteria will determine which patients had at least 1 PCSA during the on-treatment period, taking into account all evaluations performed during the on-treatment period, including unscheduled or repeated evaluations. The number of all such patients will be the numerator for the on-treatment PCSA percentage.

#### **11.4.3.1 Analysis of adverse event data**

Treatment-emergent AEs, treatment-emergent SAEs, TEAEs leading to treatment discontinuation and treatment-emergent AESIs will be summarized for each treatment group based on MedDRA coding of verbatim terms reported by investigators.

Adverse event incidence tables will present by system organ class (SOC) (sorted by internationally agreed order), high-level group term (HLGT), high level term (HLT) and preferred term (PT) sorted in alphabetical order for each treatment group, the number (n) and percentage (%) of patients experiencing an AE. Multiple occurrences of the same event in the same patient will be counted only once in the tables within a treatment period. The denominator for computation of percentages is the safety population within each treatment group.

Treatment-emergent AESI, by AESI category and PT, will show number (%) of patients overall, sorted by decreasing incidence of PT within each AESI category. The AESIs include, but are not limited to, the following categories and details of the MedDRA coding will be provided in the statistical analysis plan: Neutropenia, thrombocytopenia, infections, hepatic disorders, diverticulitis/GI ulcerations/GI perforations, elevation in lipids, systemic allergic reactions, malignancy, autoimmune or drug-induced lupus like syndrome and demyelinating disorders.

Death: The following deaths summaries will be generated:

- Number (%) of patients who died by study period (TEAE, on-study) summarized on the safety population by treatment received.
- Death in nonrandomized patients or randomized and not treated patients.
- TEAE leading to death (death as an outcome on the AE CRF page as reported by the Investigator) by primary SOC , HLGT, HLT and PT showing number (%) of patients sorted by internationally agreed order of SOC and alphabetic order of HLGT, HLT, and PT.

#### **11.4.3.2 Analysis of laboratory data**

The summary statistics (including number, mean, median, SD, minimum and maximum) of all laboratory variables will be calculated for each visit or study assessment (baseline, each post-

baseline time point, endpoint) by treatment group. Listings will be provided with flags indicating the out of range values as well as the PCSA values.

The incidence of PCSA at any time will be summarized by treatment group for each laboratory parameter. Shift tables showing changes with respect to the baseline status will be provided.

#### 11.4.3.2.1.1 Neutropenia

The incidence of neutropenia by maximal grade (lowest neutrophils value reported) during the TEAE period will be summarized. The 4 grades are defined as below:

- Grade 1:  $\geq 1.5$  Giga/L – LLN.
- Grade 2:  $\geq 1.0$  – 1.5 Giga/L
- Grade 3:  $\geq 0.5$  – 1.0 Giga/L.
- Grade 4:  $< 0.5$  Giga/L.

For patients with Grade 3 or 4 neutropenia, a listing with the individual neutropenia counts, and selected laboratory tests at each visit (including unscheduled visits for retest) will be provided. In addition, the neutrophil counts at each scheduled visit during the study will be plotted by treatment groups. Dose will be reduced to 150 mg if patient was randomized to the 200 mg group.

#### 11.4.3.2.1.2 Assessment of potential drug-induced liver injury

The liver function tests, namely ALT, AST, alkaline phosphatase and total bilirubin, are used to assess possible drug induced liver toxicity. The proportion of patients with PCSA values at any post-baseline visit by baseline status will be displayed by treatment group for each parameter. The proportion of patients with PCSA values at any post-baseline visit will also be displayed by duration of exposure for each treatment group.

Time to onset of the initial ALT elevation ( $> 3$  x ULN), time to onset of the initial AST elevation ( $> 3$  x ULN), time to onset of the initial total bilirubin elevation ( $> 2$  x ULN), and time to first observation of ALT  $> 3$ ULN or Total Bilirubin  $> 2$  ULN (whichever comes first) will be analyzed using Kaplan-Meier estimates, using the midpoint of the time interval between the first assessment showing the elevation and the previous assessment, presented by treatment group. A graph of distribution of peak values of ALT versus peak values of total bilirubin will also be presented. Note that the ALT and Total bilirubin values are presented on a logarithmic scale. The graph will be divided into 4 quadrants with a vertical line corresponding to 3 x ULN for ALT and a horizontal line corresponding to 2 x ULN for total bilirubin.

Summarize the normalization by parameter (to  $\leq 1$  ULN or return to baseline) of elevated LFTs by categories of elevation (1- $< 3$  x, 3 x, 5 x, 10 x, 20 x ULN for ALT and AST, 1.5 x ULN for Alkaline phosphatase, and 1.5 x and 2 x ULN for total bilirubin), with following categories of normalization: never normalized, normalized after IMP discontinuation. Note that a patient will be counted only under the maximum elevation category. 1-3, 3-5, 5-10, 10-20,  $> 20$ .

The incidence of liver-related AEs will be summarized by treatment group. The selection of preferred terms will be based on standardized MedDRA query (SMQ) Hepatic disorder. Time to liver-related treatment discontinuation and time to liver death may also be provided based on hepatic disorder SMQ.

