##### **10.4.1 Temporary treatment discontinuation with investigational medicinal product (sarilumab or matching placebo)**

Temporary treatment discontinuation may be considered because of suspected AEs. Re initiation of treatment with the IMP (SC and/or oral) will be done under close and appropriate clinical/and or laboratory monitoring once it is considered that the responsibility of the IMP(s) in the occurrence of the concerned event was unlikely and if the selection criteria for the study are still met (refer to [Section 7.1](#) and [Section 7.2](#)).

Temporary SC IMP treatment discontinuation corresponds to  $\geq 1$  dose not administered to the patient.

A temporary discontinuation of SC IMP  $\geq 31$  consecutive days will be considered permanent.

The following is a list of criteria for temporary discontinuation (refer to [Section 10.8](#) for details):

- Increase in ALT level to  $\geq 3$  x ULN to  $\leq 5$  x ULN and total bilirubin  $\leq 2$  x ULN will result in temporary IMP discontinuation. The IMP (sarilumab or matching placebo) can be resumed only after the ALT has returned to a value  $< 3$  x ULN and all requirements for resumption of study drug administration are met based on investigator's judgement. The IMP may be resumed at the same dose or at a lower dose of 150 mg q2w in such cases if the patient was randomized to the 200 mg group (see [Section 10.8.2](#) and [Appendix E](#)).
- Decrease in neutrophil count to a level  $\geq 500/\text{mm}^3$  to  $< 1000/\text{mm}^3$  without signs of infection. The IMP (sarilumab or matching placebo) can be resumed only after the neutrophils have returned to a value  $\geq 1000/\text{mm}^3$  and all requirements for resumption of study drug administration are met based on investigator's judgement. The IMP may be

resumed at the same dose or at a lower dose of 150 mg q2w in such cases if the patient was randomized to the 200 mg group (see [Section 10.8.3](#) and [Appendix E](#)).

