### 10.8.2 Liver function tests

Please refer to [Section 10.5.5](#) for liver function test (LFT) abnormalities to be reported as AESI.

The Sponsor relies on investigators', particularly Safety Assessors', judgment for adapting concomitant medication in case of LFT abnormalities.

In order to closely follow LFTs, assessment of ALT, AST, alkaline phosphatase, and bilirubin (total, conjugated) are performed per specifications on the study flow charts (see flow chart [Section 1.2](#)).

- The IMP (sarilumab or matching placebo) should be permanently discontinued in case of confirmed ALT  $>5$  x ULN or in case of confirmed ALT  $>3$  x ULN and total bilirubin  $>2$  x ULN (unless the patient has documented Gilbert's disease). A complete serological and ultrasonography work-up should be conducted in case of ALT  $>5$  x ULN or ALT  $>3$  x ULN and concomitant total bilirubin  $>2$  x ULN (see [Appendix E](#)).
- If ALT is  $\geq 3$  x ULN and  $\leq 5$  x ULN and bilirubin is  $\leq 2$  x ULN, administration of SC IMP must be temporarily interrupted, and LFTs must be repeated within 48 hours from the study Investigator's awareness for confirmation of transaminase levels. If the elevated ALT level is confirmed but stays below the 5 x ULN thresholds, then LFTs must be repeated according to the provided guideline and at a minimum of every 7 days until conditions for resumption of SC IMP administration are met (see [Appendix E](#)).
- The SC IMP will then be restarted at the Safety Assessor's discretion after conditions for resumption of IMP administration are met (ALT  $<3$  x ULN). Safety assessor will have the options of either to restart the SC IMP at its current dose or to perform a dose reduction

request in a blinded manner through IRT for patients without a previous reduction in dose. Dose of sarilumab will then be reduced to 150 mg if the patient was randomized to the 200 mg group.

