- Grade 2: ≥ 1.0 Giga/L- < 1.5 Giga/L.
- Grade 3: ≥ 0.5 Giga/L- < 1.0 Giga/L.
- Grade 4: < 0.5 Giga/L.

Thrombocytopenia

The incidence of thrombocytopenia by maximal grade (lowest platelet count reported during the TEAE period) as defined below will be summarized.

- ≥ 75 Giga/L-100 Giga/L.
- ≥ 50 Giga/L- < 75 Giga/L.
- ≥ 25 Giga/L- < 50 Giga/L.
- < 25 Giga/L.

Hepatic disorders

The liver function tests, namely AST, ALT, ALP, and total bilirubin are used to assess possible drug-induced liver toxicity. The proportion of patients with PCSA values at any post-baseline visit by baseline status will be displayed by treatment group for each parameter. The proportion of patients with PCSA values at any post baseline visit may be displayed by duration of exposure for each treatment group.

A graph of distribution of peak values of ALT versus peak values of total bilirubin will also be presented. Note that the ALT and total bilirubin values are presented on a logarithmic scale. The graph will be divided into 4 quadrants with a vertical line corresponding to 3x ULN for ALT and a horizontal line corresponding to 2x ULN for total bilirubin.

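### The protocol's liver-test normalization summary has no category for recovery on continued drug, and the SAP drops it and the hepatic SMQ table without saying so

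*Protocol*

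**What the plan says.** Protocol 11.4.3.2.1.2 commits to a normalization summary for each liver test, where normal means at or below 1 x ULN or back to baseline. Patients are grouped by their maximum elevation, and for ALT and AST the lowest band runs from 1 to just under 3 x ULN. Outcomes are to be shown "with following categories of normalization: never normalized, normalized after IMP discontinuation"; no other outcome is named. The same section adds: "The incidence of liver-related AEs will be summarized by treatment group", with preferred terms taken from the Hepatic disorder SMQ. Protocol 11.4.3.1 lists hepatic disorders among the AESI categories and says that "details of the MedDRA coding will be provided in the statistical analysis plan".

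The management text matters here because it determines which outcomes can occur. For ALT of 3 to 5 x ULN with bilirubin no higher than 2 x ULN, Protocol 10.8.2 says that "administration of SC IMP must be temporarily interrupted, and LFTs must be repeated within 48 hours from the study Investigator's awareness". Once ALT is below 3 x ULN, "The SC IMP will then be restarted at the Safety Assessor's discretion after conditions for resumption of IMP administration are met".

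SAP 2.4.5.3, under Hepatic disorders, opens with "The liver function tests, namely AST, ALT, ALP, and total bilirubin are used to assess possible drug-induced liver toxicity". It then gives PCSA proportions by baseline status, an optional display by duration of exposure, and the plot of peak ALT against peak bilirubin. It has no normalization summary and no SMQ-based table of liver events.

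**The concern.** Protocol section 4 names clinically evident hepatic injury with raised transaminases as an important potential risk of sarilumab. To judge that risk, a reader needs to know whether elevations settled on continued dosing, during a hold, only after stopping, or not at all. The protocol's two outcomes cannot separate these courses. A test that normalizes on drug must either be counted as never normalized, which overstates persistence, or be left out of the table. The SAP then omits the summary altogether, together with the pooled count of liver-related events by arm, and nothing in the SAP tells the reader that two planned safety analyses are gone.

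**Working it through.** The plan gives no figure to reproduce, so the check sets the sections side by side.

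**1. Possible courses of an elevated test**

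| Course | Protocol category | Summarized in SAP |
|---|---|---|
| Never normalizes | Yes | No |
| Normalizes while SC IMP continues | None | No |
| Normalizes during a temporary hold | Only if a hold counts as discontinuation | No |
| Normalizes after permanent discontinuation | Yes | No |

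Of four courses, the protocol clearly covers two, leaves one unclear and has no place for one. The SAP tabulates none.

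**2. Is recovery on drug an expected course?** In Protocol 10.4.1 and 10.8.2 the hold starts at ALT 3 x ULN. In 10.4.3 the permanent stop applies to ALT above 5 x ULN, or above 3 x ULN with bilirubin above 2 x ULN. The lowest band of the summary, 1 to just under 3 x ULN, lies below all of these. Investigators may still stop treatment on their own judgment, but by default dosing continues, so a recovery in that band normally happens on drug.

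**3. Recovery after a restart.** Protocol 10.4.1 states: "The IMP (sarilumab or matching placebo) can be resumed only after the ALT has returned to a value" below 3 x ULN. Normalization requires 1 x ULN or baseline. A patient restarted while still between those levels can first normalize on resumed drug, which again has no category.

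**4. The hold itself.** Protocol 10.4.1 uses the word discontinuation for a hold: "Temporary treatment discontinuation may be considered because of suspected AEs". The second category could therefore include recovery during a hold. If it does, such patients are merged with those who recovered only after stopping for good.

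**5. What the SAP keeps**
- SAP 2.4.5.3: values and changes from baseline by visit, plots of means, PCSA incidence, shift tables, Kaplan-Meier time to first elevation, and flagged listings.
- SAP 2.1.4.1 (Table 3) and 2.4.5.1: ALT of at least 3 x ULN, and ALT increase leading to permanent discontinuation, as AESIs. Within each AESI category the displays cover seriousness, treatment discontinuation, death and relatedness, but not recovery.
- SAP 2.4.5.1: all TEAEs by SOC, HLGT, HLT and PT.

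Table 3 has no hepatic disorders category. A liver event that meets neither ALT criterion appears only in the general tables, with no pooled count. SAP 2.4.8 does specify SMQs for hypersensitivity and anaphylaxis, so the method is in use elsewhere in the plan.

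**6. Declaration.** SAP 1.5 lists the consequences of amendment 02. SAP 1.6 lists the SAP's own modifications: COVID-19 summaries and the PMR activity score. Neither mentions these removals.

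**7. Elevations with no later value.** Chemistry after baseline is scheduled at Weeks 4, 12, 24, 40 and 52. Protocol 10.2.3.1 has none at Week 58. A mild elevation first seen at Week 52 may therefore have no later value, and should not be counted with tests that were followed and stayed high.

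**The case against.** The strongest reply is that little is lost. The SAP keeps the displays listed above and goes beyond the protocol in places: it adds onset of ALT and AST above 5 x ULN, and its Appendix C has ALT and AST bands starting just above 1 x ULN. Because the SAP does not produce the two-category table, no patient is misclassified under it. The analyses are descriptive, and neither the primary endpoint nor patient monitoring is affected.

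Much of this stands, and it limits the point. A reader might infer that hepatic harm goes unreported, or that its consequences do. The documents do not support that: seriousness, discontinuation and death are shown for the ALT-based AESIs, and the course over time is visible in group means and individual listings. A reader might also infer that recovery during a hold is certainly excluded from the protocol's categories. Protocol 10.4.1 makes that an ambiguity, not an established gap.

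What does not stand is the idea that the remaining outputs replace the missing ones. Means by visit do not follow individual elevations, shift tables set baseline status against abnormality at any time, and listings are not a summary by arm. The misclassification is hypothetical only because the SAP dropped the table; restoring it as the protocol words it would make it real.

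**Conclusion.** The point holds in a limited form. The protocol's normalization summary has no category for recovery on continued drug and does not define how a hold is treated. The SAP omits that summary and the Hepatic disorder SMQ table without listing either removal. The result is that the SAP has no summary of whether liver-test elevations resolved, and no pooled SMQ count of liver-related events by arm.

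The size is two descriptive safety tables. A reader might apply an assumed rate of ALT elevation to the 59 patients per group and call the result the number misclassified. That would count everyone with any elevation, whatever their course, and the documents give no rate of elevation or of recovery. No patient count is supported.

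The conclusion rests on the text of Protocol 10.4.1, 10.4.3 and 10.8.2 for what happens below 3 x ULN; the flow charts in Appendix E are not reproduced in the copy reviewed.

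**What to change.** Change the SAP only, and reporting only; no dosing, hold or stopping rule is touched.

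1. In SAP 2.4.5.3, Hepatic disorders, restore the normalization table by arm and maximum elevation, with mutually exclusive outcomes:
   - normalized while SC IMP continued, including after a restart
   - normalized during a temporary interruption
   - normalized after permanent discontinuation or end of treatment
   - not normalized, with a later value available
   - no later value
2. Assign the outcome by dosing status on the date of the first normalized value.
3. Keep the threshold in Protocol 11.4.3.2.1.2 (at or below 1 x ULN, or baseline). Note that it differs from Appendix E, whose monitoring instruction describes normal as below 2 x ULN.
4. Restore the Hepatic disorder SMQ incidence table by arm.
5. Record in SAP 1.6 the departure from the protocol's category list. If the sponsor prefers to leave either table out, declare and justify that there.

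The cost is SAP wording and two descriptive tables, built from liver tests, dosing dates and coded adverse events already collected. A protocol amendment is not needed; it would require ethics approval under Protocol section 15, and SAP 1.1 records that the last patient's last visit has already taken place.
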